6.2.13 Mean Pulmonary Arterial Pressure

The mPAP will be measured at the pre-PEA visit (Visit 2) and at the 6-month follow-up visit after PEA (Visit 4). The mPAP value at screening will be collected from the medical history of the patient.

6.2.14 Pulmonary Artery Wedge Pressure

The PAWP will be measured at the pre-PEA visit (Visit 2) and at the 6-month follow-up visit after PEA (Visit 4). The PAWP value at screening will be collected from the medical history of the patient. If the PAWP measurement is not available prior to screening, the left ventricular end diastolic pressure will be used to record wedge pressure at screening.

6.2.15 Length of Stay in Hospital and Intensive Care Unit

The length of stay in hospital and ICU in days after PEA during Visit 3 will be reported for each patient.

6.2.16 Time on Mechanical Ventilation

The total time spent on mechanical ventilation from the start of the ICU stay until end of mechanical ventilation during Visit 3 will be reported for each patient.

6.3 Safety Assessments

Safety assessments include AEs, vital sign measurements, ECG measurements, physical examinations, clinical laboratory examinations, and pregnancy testing. During the double-blind treatment period, patients will visit the study site at baseline (Visit 1) and at time points specified in the Schedule of Events (Table 12-1).

6.3.1 Adverse Events

6.3.1.1 Definitions of Adverse Events

The investigator is responsible for reporting all AEs that are observed or reported during the study, regardless of their relationship to study drug or their clinical significance.

An AE is defined as any untoward medical occurrence in a patient enrolled into this study regardless of its causal relationship to study drug. Patients will be instructed to contact the investigator at any time after randomisation if any symptoms develop.

A TEAE is defined as any event not present before exposure to study drug or any event already present that worsens in either intensity or frequency after exposure to study drug.

An SAE is defined as any event that results in death, is immediately life threatening, requires inpatient hospitalisation or prolongation of existing hospitalisation, results in persistent or significant disability/incapacity, or is a congenital anomaly/birth defect. Important medical events that may not result in death, be life threatening, or require hospitalisation may be considered SAEs when, based upon appropriate medical judgment, they may jeopardise the patient or may require medical or surgical intervention to prevent one of the outcomes listed in this definition. Examples of such medical events include allergic bronchospasm requiring intensive treatment in an emergency room or at home, blood dyscrasias or convulsions that do not result in inpatient hospitalisation, or the development of drug dependency or drug abuse.

6.3.1.2 Eliciting and Documenting Adverse Events

Adverse events will be assessed from the time the patient signs the ICF until exit from the study.

At every study visit, patients will be asked a standard nonleading question to elicit any medically related changes in their well-being. They will also be asked if they have been hospitalised, had any accidents, used any new medications, or changed concomitant medication regimens (both prescription and over-the-counter medications).

In addition to patient observations, AEs identified from any study data (eg, laboratory values, physical examination findings, ECG changes) or identified from review of other documents that are relevant to patient safety will be documented on the AE page in the eCRF.

6.3.1.3 Reporting Adverse Events

All AEs reported or observed during the study will be recorded on the AE page in the eCRF. Information to be collected includes drug treatment, dose, event term, time of onset, investigator-specified assessment of severity and relationship to study drug, time of resolution of the event, seriousness, any required treatment or evaluations, action taken with the study drug, and outcome of the event (recovered/resolved, recovering/resolving, recovered/resolved with sequelae, fatal, or unknown). Adverse events resulting from concurrent illnesses, reactions to concurrent illnesses, reactions to concurrent medications, or progression of disease states must also be reported. All AEs will be followed to adequate resolution. The Medical Dictionary for Regulatory Activities will be used to code all AEs.

Any medical condition that is present at the time that the patient is screened but does not deteriorate should not be reported as an AE. However, if it deteriorates at any time during the study, it should be recorded as an AE.

Any AE that meets SAE criteria (Section 6.3.1.1) must be reported to PPD pharmacovigilance immediately (ie, within 24 hours) after the time site personnel first learn about the event. The following contact information is to be used for SAE reporting:

PPD pharmacovigilance

SAE Hotline: [name]

SAE Fax line: [name]

6.3.1.4 Assessment of Severity

The severity, or intensity, of an AE refers to the extent to which an AE affects the patient's daily activities. The intensity of the AE will be rated as mild, moderate, or severe using the following criteria:

Mild: An event usually transient in nature and generally not interfering with normal activities.

Moderate: An AE that is sufficiently discomforting to interfere with normal activities.

Severe: An AE that is incapacitating and prevents normal activities.

Changes in the severity of an AE should be documented to allow an assessment of the duration of the event at each level of intensity to be performed.

6.3.1.5 Assessment of Causality

The investigator's assessment of an AE's relationship to study drug is part of the documentation process, but it is not a factor in determining what is or is not reported in the study. If there is any doubt as to whether a clinical observation is an AE, the event should be reported.

The relationship or association of the study drug in causing or contributing to the AE will be characterised using the following classification and criteria:

Unrelated: This relationship suggests that there is no association between the study drug and the reported event.

Possible: This relationship suggests that treatment with the study drug caused or contributed to the AE, ie, the event follows a reasonable temporal sequence from the time of drug administration or follows a known response pattern to the study drug, but could also have been produced by other factors.

Probable: This relationship suggests that a reasonable temporal sequence of the event with drug administration exists and, based upon the known pharmacological action of the drug, known or previously reported adverse reactions to the drug or class of drugs, or judgment based on the investigator's clinical experience, the association of the event with the study drug seems likely. The event disappears or decreases on cessation or reduction of the dose of study drug.

Definite: This relationship suggests that a definite causal relationship exists between drug administration and the AE, and other conditions (concurrent illness, progression/expression of disease state, or concurrent medication reaction) do not appear to explain the event. The event reappears or worsens if the study drug is readministered.

6.3.1.6 Exceptions

The hospitalisation due to study-related procedures ie, for scheduled RHC and PEA will not be considered as an SAE for this study.

6.3.1.7 Adverse events of special interest

Adverse events of special interest will be separately analysed and closely monitored throughout the course of the study for safety reasons.

Adverse events of special interests are defined as myocardial infarction, haemorrhage, hypotension, haemoptysis, syncope and stroke.

6.3.1.8 Follow-Up of Patients Reporting Adverse Events

All AEs must be reported in detail on the appropriate page in the eCRF and followed to satisfactory resolution, until the investigator deems the event to be chronic or not clinically significant, or until the patient is considered to be stable.

6.3.2 Vital Sign Measurements

Vital signs, including blood pressure, heart rate, respiration, and body temperature will be obtained with the patient in a supine or seated position after resting for approximately 5 minutes. Vital signs will be measured as mentioned in Table 12-1.

6.3.3 Electrocardiogram Measurements

Twelve-lead ECGs will be performed to calculate the HR, and PR, QRS, QT, and QT interval Fridericia correction (QTcF) will also be calculated. The ECGs will be obtained

with the patient in the supine position, prior to blood draws, and after the patient has been supine for at least 10 minutes. Electrocardiograms will be measured as mentioned in Table 12-1.

All standard 12-lead ECGs will be recorded and analysed locally at the site by the investigator.

6.3.4 Physical Examinations

A complete physical examination including assessments of the head, eyes, ears, nose, throat, skin, neck (including thyroid), lungs, cardiovascular system, abdomen, lymph nodes, and extremities will be obtained at screening. A physical examination including updates since the screening visit with focus on previously noted abnormalities in organ systems, including skin and hair, will be completed at time points specified in schedule of events (Table 12-1).

6.3.5 Clinical Laboratory Testing

Laboratory assessments, including clinical laboratory testing, serum pregnancy test, and hepatitis B virus, hepatitis A immunoglobulin M, hepatitis C antibody, and human immunodeficiency virus screen will be performed at time points specified in Schedule of Events (Table 12-1).

- Routine clinical laboratory testing will be performed by a central laboratory and will include the following:
 - Haematology: haemoglobin, haematocrit, red blood cell count, white blood cell count with differential, mean corpuscular volume, mean corpuscular haemoglobin, mean corpuscular haemoglobin concentration, and absolute platelet count;

- Clinical chemistry: total protein, sodium, potassium, calcium, chloride, inorganic phosphate, albumin, fasting blood glucose, glycated haemoglobin, high-density lipoprotein and low-density lipoprotein cholesterol, triglycerides, blood urea nitrogen, creatinine (and creatinine clearance by the Cockcroft-Gault formula), uric acid, bilirubin (total and direct), alkaline phosphatase, aspartate aminotransferase, alanine aminotransferase, γ glutamyltransferase, lactate dehydrogenase, creatine kinase, cardiovascular marker panel, and high-sensitivity C-reactive protein;
- Urinalysis: appearance, colour, pH, specific gravity, glucose, blood, bilirubin, leukocyte esterase, ketones, nitrates, urine protein, urine creatinine, protein/creatinine ratio. Microscopic urinalysis will be performed if urinalysis results are abnormal.
- Serum pregnancy testing will be performed for all women of childbearing potential as mentioned in Table 12-1.

6.3.6 Clinical Significance of Safety Assessments

Any abnormal laboratory test results (haematology, clinical chemistry, or urinalysis) or other safety assessments (eg, ECGs, vital sign measurements, physical examinations), including those that worsen from baseline, and are felt to be clinically significant in the medical and scientific judgment of the investigator, are to be recorded as AEs or SAEs.

However, any clinically significant safety assessments that are associated with the underlying disease, unless judged by the investigator to be more severe than expected for the patient's condition, are not to be reported as AEs or SAEs.

If any of the laboratory parameters of interest show a significant shift from baseline, patients will then be scheduled for an interim visit within 2 weeks to have the laboratory measurements repeated.

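### Protocol 6.3.6 conditionally exempts disease-associated safety findings from AE and SAE reporting, contradicting the reporting rules in 6.3.1.1 to 6.3.1.5

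*Protocol*

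**What the plan says.** Protocol 6.3.6 has two relevant paragraphs. The first says that abnormal laboratory results and other safety assessments which the investigator finds clinically significant are recorded as AEs or SAEs. Its scope includes "vital sign measurements, physical examinations), including those that worsen from baseline". The second takes part of that back. It concerns "any clinically significant safety assessments that are associated with the underlying disease" and provides that these, with an exception for findings the investigator considers worse than the patient's condition would explain, "are not to be reported as AEs or SAEs".

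The general reporting sections have no such exemption:

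- Protocol 6.3.1.1 makes the investigator "responsible for reporting all AEs that are observed or reported during the study, regardless of their relationship to study drug or their clinical significance".
- Protocol 6.3.1.2 sends to the AE page "AEs identified from any study data (eg, laboratory values, physical examination findings, ECG changes" and similar sources).
- Protocol 6.3.1.3 states: "Adverse events resulting from concurrent illnesses, reactions to concurrent illnesses, reactions to concurrent medications, or progression of disease states must also be reported". It also treats a condition present at screening as an AE once it deteriorates, and requires SAEs to be reported within 24 hours.
- Protocol 6.3.1.5 says the causality assessment does not decide what is reported, and that a doubtful observation should be reported.
- Protocol 6.3.1.7 lists the AEs of special interest: "Adverse events of special interests are defined as myocardial infarction, haemorrhage, hypotension, haemoptysis, syncope and stroke".

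SAP 9.1 repeats the broad rule and does not carry the exemption.

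**The concern.** The exemption depends on two judgements by the investigator: that the finding belongs to the disease, and that it is no worse than expected. The protocol gives no criteria for either. In this population disease attribution is readily available, because Protocol 1.1 describes CTEPH as leading to right ventricular failure.

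Protocol 3.1.1 justifies the placebo arm partly because it allows drug effects to be separated from disease effects. That works only if events are recorded first and compared between arms afterwards. Under 6.3.6 the attribution can be made patient by patient before anything reaches the AE page. What is at stake is the completeness of the AE, SAE and special-interest tables and, for findings that meet SAE criteria, the 24-hour report.

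**Working it through.** No arithmetic applies to the contradiction itself. The check takes one test case through the rules and then through the planned tables.

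**Test case.** A laboratory, ECG, vital-sign or examination finding has worsened since baseline. It is clinically significant, the investigator associates it with CTEPH, and it is judged no more severe than expected.

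**Step 1: apply each rule.**

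| Protocol section | Instruction for the test case |
|---|---|
| 6.3.1.1 | Report: relationship to drug and clinical significance do not matter |
| 6.3.1.2 | Document: AEs found in study data go on the AE page |
| 6.3.1.3 | Report: progression and any deterioration count, with no expectedness threshold |
| 6.3.1.5 | Attribution is not a ground for leaving an event out |
| 6.3.6, paragraph 1 | Record as AE or SAE |
| 6.3.6, paragraph 2 | Do not report |

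The severity exception in 6.3.6 does not remove the conflict. It brings back only findings worse than expected, whereas 6.3.1.3 is triggered by any deterioration.

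**Step 2: look for a rule of precedence.** Protocol 6.3.1.6, headed Exceptions, covers only hospitalisation for scheduled RHC and PEA. Protocol 6.3.7 asks for prompt notification of all SAEs and non-serious AEs. Protocol 6.3.1.7 does not say that events of special interest override 6.3.6. SAP 9.1 and 9.1.4 do not mention the exemption. Nothing states which rule governs.

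**Step 3: check that SAEs are within reach.** The first paragraph of 6.3.6 itself foresees findings recorded as SAEs, and the second names SAEs among the things not to be reported. The overlap with the 24-hour rule is therefore in the text, although most SAEs are clinical events rather than assessment findings.

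**Step 4: trace an unreported finding through the SAP.**

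- AE, SAE and special-interest tables (SAP 9.1.1 to 9.1.7) count recorded TEAEs. An unreported finding is absent.
- Laboratory: observed values, changes from baseline and shift tables with the worst postbaseline value remain (SAP 9.2). The protocol's table of investigator-judged clinically significant values is removed (SAP 11, item 3), which leaves the AE page as the only place for that judgement.
- ECG: clinically significant abnormal results are tabulated by arm (SAP 9.4), independently of AE recording.
- Vital signs: summarised by arm and scheduled visit (SAP 9.3). Table 12-1 has no scheduled site visit between Day 1 and Visit 2 at Day 90+30. Titration in that interval uses home blood pressure (Protocol 5.2), for which the SAP describes no summary.
- Physical examination: summarised by arm and body system (SAP 9.5).

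The loss is therefore to event counts. Most underlying scheduled values survive.

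**Step 5: size.** The documents give no rate at which findings would be attributed to disease and left off the AE page, so no expected number of missing events can be derived.

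**The case against.** The strongest case on the other side is that this is a narrow wording problem with several safeguards around it. Much of that stands.

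- A reader might infer that 6.3.6 bans disease-related events outright. It does not. The exemption is conditional on severity and covers assessment findings only. Patient-reported events such as dizziness or syncope remain under 6.3.1.1 to 6.3.1.3.
- A reader might infer that the hypotension signal will be lost. The documents do not support that. Hypotension is a named event of special interest, Protocol 1.5 describes it as a risk with riociguat, symptomatic hypotension is excluded at entry, its symptoms are reportable in their own right, and 6.3.1.5 says to report when in doubt. What remains is an isolated low reading confidently put down to disease. It is also arguable whether home readings count as safety assessments under 6.3.6.
- A reader might want to size the loss from the 12-week open-label study in Protocol 1.4, where hypotension was reported in 11 of 75 patients. With 88/2 = 44 per arm, 44 × 11/75 is about 6.5 patients. That is a reporting rate in a mixed PAH and CTEPH population. It says nothing about how many events 6.3.6 would remove, and any assumed fraction, including one near zero, has no basis in the documents.
- A reader might infer bias in favour of riociguat. Investigators are blinded (Protocol 5.6), and no mechanism is shown that would affect one arm more than the other.
- The DSMB sees unblinded safety data and other study information (Protocol 3.1 and 6.5), not only AE tables.

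None of these points tells a site which instruction to follow for the test case. The report-if-in-doubt rule does not help an investigator who has no doubt that the disease is the cause.

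**Conclusion.** Wrong as written: an internal contradiction. For clinically significant laboratory, ECG, vital-sign or examination findings that are associated with the disease and no worse than expected, Protocol 6.3.6 cannot be followed together with 6.3.1.1 to 6.3.1.5, and neither document resolves it. The consequence is possible under-recording in the AE, SAE and special-interest comparisons. It is clearest for laboratory findings, where the separate table of clinical significance has been dropped.

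The size is unknown. The conclusion rests on the text alone and assumes only that some sites will follow 6.3.6 as worded. It does not claim that a safety signal will be missed or that the comparison is biased in a particular direction.

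**What to change.** Reconcile Protocol 6.3.6 with 6.3.1.1 to 6.3.1.5. The cleanest change is to delete its second paragraph. If the sponsor wants to keep some exemption, the minimum is to state three things:

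1. It never applies to an event that meets SAE criteria.
2. It never applies to an AE of special interest as listed in 6.3.1.7.
3. Attribution to the underlying disease is recorded in the causality assessment under 6.3.1.5 and is not a reason for non-reporting.

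Under the minimum option, 6.3.1.1 to 6.3.1.3 should also refer to whatever exemption remains, so that the sections agree. SAP 9.1 already carries the broad rule and needs no change if the paragraph is deleted.

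The cost is a one-paragraph protocol edit, handled under the amendment process in Protocol 10.2.1, a notice to the four sites, and some additional disease-related AE entries. No dose, visit, endpoint or analysis set changes.

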6.3.7 Regulatory Reporting Requirements for Serious Adverse Events

Prompt notification by the investigator to the sponsor or its representative of all SAEs and non-serious AEs occurring during a clinical trial is essential so that legal obligations and ethical responsibilities towards the safety of subjects and the safety of a product under clinical investigation are met.

The sponsor has a legal responsibility to notify both the local regulatory authority and other regulatory agencies about the safety of a product under clinical investigation. The sponsor will comply with country-specific regulatory requirements relating to safety reporting to the regulatory authority, Institutional Review Board (IRB)/Independent Ethics Committee (IEC) and investigators.

6.4 Pregnancy

Pregnancy is not regarded as an AE unless there is a suspicion that an investigational product may have interfered with the effectiveness of a contraceptive medication. Any pregnancy that occurs during study participation must be reported to PPD pharmacovigilance using pregnancy report form. To ensure patient safety, each pregnancy must be reported to ICA within 2 weeks of learning of its occurrence. The pregnancy must be followed-up to determine outcome (including spontaneous miscarriage, elective termination, normal birth, or congenital abnormality) and status of mother and child, even if the patient was discontinued from the study. Pregnancy complications and elective terminations for medical reasons must be reported as an AE or SAE. Spontaneous miscarriages must be reported as an SAE.

Any SAE occurring in association with a pregnancy, brought to the investigator's attention after the patient has completed the study, and considered by the investigator as possibly related to the study drug, must be promptly reported to ICA.

6.5 Safety Monitoring Committee

An unblinded, independent DSMB will periodically review safety data. The frequency of data review and DSMB processes are outlined in the DSMB charter. In brief, the DSMB will meet before study start, after approximately 8 subjects have completed at least 12 weeks of study drug treatment and undergone PEA, after approximately 20 subjects have completed at least 12 weeks of study drug treatment and undergone PEA and after approximately 20 subjects have completed the study. An optional meeting is scheduled after 30–40 patients have completed the study. The DSMB will periodically review unblinded study information during the conduct of the study. If necessary, unblinding of individual patient data and treatment groups may be done.

6.6 Sample Collections

All visits that include clinical laboratory safety assessments must be after an 8-hour fast.

Sample collection, processing, and shipping should be performed according to the central/local laboratory requirements.

7 Statistical and Analytical Plan

Due to the investigative nature of this study, all statistical analyses will be exploratory. A clearly defined statistical analysis plan (SAP) will be generated separately to provide a more detailed description of the planned statistical analyses in order to meet the objectives of the registry. The SAP will be finalised before database lock and the breaking of the study blind. Further specific analyses for publications will be prespecified in separate plans or documents.

